9.2.1. Adverse Events of Interest

The AEs of interest include the following:

- Hypotension
- Acute Bronchospasm
- Hypoxia
- Tachycardia
- Acute Urticaria

These AEs of interest are commonly seen with inhaled products. If AEs of interest occur at a Grade 3 level or higher in two or more subjects in a cohort, then an additional 4 subjects (3 active, 1 placebo) may be added to the cohort. Any of the Grade ≥ 3 toxicities for the AEs of interest as well as any other respiratory AEs reported, will be evaluated and considered when making dose escalation decisions. If no additional subjects experience any Grade ≥ 3 AEs of Interest, dose escalation may proceed (if recommended by the SMC).

In addition, a dose-limiting toxicity (DLT) is defined as follows, determined by the Investigator as study drug related:

- Allergic reaction requiring urgent medical intervention
- Acute bronchospasm requiring urgent medical intervention
- Hypotension accompanied by other evidence of a systemic inflammatory reaction or sepsis
- Other acute AEs requiring urgent medical intervention

9.3. Laboratory Evaluations

Laboratory measurements (hematology, chemistry, urinalysis, and coagulation) obtained at baseline and each study visit will be summarized by dose group in the following ways:

- Descriptive statistics of actual results and changes from baseline (number of subjects, mean, standard deviation, median, minimum, and maximum) for the continuous data and frequencies and percentages for the categorical data, for each assessment visit

This document is confidential.

- Potentially clinically significant lab abnormalities for hematology, chemistry and coagulation will be summarized by study part, dose group and assessment visit.
- By-subject line plots will be presented by lab parameter, study part and dose group, to allow for significant out of range values to be further identified

By-subject safety laboratory listings will be generated incorporating information and assessment results obtained from the designated laboratory which provided normal range and reported out of range results. All laboratory results in SI units will be presented in data listings. Tests will be listed in alphabetical order within their respective panels (hematology, serum chemistry, urinalysis, and coagulation).

Potentially clinically significant hematology and chemistry laboratory results will be summarized using severity grades according to NCI CTCAE (version 5.0 or higher) where applicable. The worst post-baseline severity grade will be summarized and is defined as the most severe toxicity grade of the specific parameter assessed during the study at a scheduled or unscheduled visit. If a severity grade scale is missing for a laboratory parameter, the normal ranges of the clinical laboratory will be used.

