6.4. Visit Windows

There will be no derivation for visit windows in terms of summary assessments. Nominal visits will be used for by-visit tables.

For data with repeated observations at a given visit, for example, laboratory assessments, the earliest of the available non-missing values at a visit should be used in summary tables. Other observations will be considered as unscheduled visits. For the purpose of tabulations, the unscheduled post-baseline values generally will be excluded from summary tables, but will be included in the listing. Unscheduled visits will be considered for analyses of worst CTCAE laboratory grades.

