9.5. ECG

A 12-lead ECG will be performed locally at the site, and obtained at Screening, and pre-dose and 1 hour post dose on Day 1 for all subjects.

A shift table of the investigators' assessment of ECG results at each visit compared with baseline values will be presented by treatment group using the following categories: normal; abnormal (not clinically significant); abnormal (clinically significant). The number and percentage of subjects in each cross-classification group of the shift table will be presented by dose group and overall. Subjects with a missing value at baseline or post baseline will not be included in the denominator for percentage calculation.

A by-subject listing will be provided, including each ECG parameter: ventricular heart rate (beats per minute [bpm]), PR interval [msec], RR interval [msec], QRS Duration [msec], QT interval [msec], QTcB interval [msec], QTcF interval [msec] and investigator's interpretation. Potentially clinically significant QTcF values will be flagged in the listing.

The number and percentage of participants with PCS and potentially clinically significant change (PCSC) values will be summarized by visit/timepoint and for any time post-baseline. Potentially clinically significant values will be identified for ECG parameters as outlined below.

Table 10.5.1: Potentially Clinically Significant Values for QT, QTcF, QTcB

This document is confidential.

ECG Parameter	Units	Criteria for PCS Values (Observed values)		Criteria for PCS values (Change from Baseline values)	
		High	Low	Increase	Decrease
QT, QTcF	msec	>450 but <=480 >480 but <=500 >500	NA	>=30 to 60 >60	NA

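### The laboratory table of worst post-baseline CTCAE grade ignores the baseline grade, so unchanged or improved abnormalities look the same as new or worsened ones

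*SAP*

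**What the plan says.** SAP Section 9.3 grades potentially clinically significant hematology and chemistry results by CTCAE and reduces each subject to one grade per parameter: "The worst post-baseline severity grade will be summarized". With its definition, the text reads: "The worst post-baseline severity grade will be summarized and is defined as the most severe toxicity grade of the specific parameter assessed during the study". The sentence goes on to include scheduled and unscheduled visits, and Section 6.4 agrees: "Unscheduled visits will be considered for analyses of worst CTCAE laboratory grades". Parameters without a CTCAE scale fall back on the laboratory range: "If a severity grade scale is missing for a laboratory parameter, the normal ranges of the clinical laboratory will be used". None of these rules mentions the baseline grade or baseline status.

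The other laboratory outputs in Section 9.3 are:
- by-visit summaries: "Descriptive statistics of actual results and changes from baseline" for continuous values, and frequencies for categorical ones;
- counts of abnormalities: "Potentially clinically significant lab abnormalities for hematology, chemistry and coagulation will be summarized by study part, dose group and assessment visit";
- plots: "By-subject line plots will be presented by lab parameter, study part and dose group";
- by-subject listings with normal ranges and out-of-range results.

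Other safety sections do refer to baseline. Section 9.2 counts an adverse event as treatment-emergent only if it is new or exacerbated after the first dose. Section 9.4 has change-from-baseline criteria for blood pressure and oxygen saturation. Section 9.5 plans a shift of the investigator's ECG assessment against baseline: "The number and percentage of subjects in each cross-classification group of the shift table will be presented by dose group and overall".

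**The concern.** These subjects have cystic fibrosis and chronic pulmonary infection, so some graded laboratory values before dosing are plausible. A table of worst post-baseline grades then mixes two kinds of subject: those whose laboratory status changed after dosing, and those who were already abnormal and stayed so. Safety and tolerability is the primary objective of both parts, and the active groups are small (3, 3, 3 and 15). In a group of 3, one unchanged abnormality reads as 1/3 = 33%.

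The definition adds a second ambiguity. The label says post-baseline, but the wording that defines it covers anything graded during the study, and screening and baseline visits are part of the study. A programmer who follows the definition rather than the label could let a pre-dose grade stand as the worst grade.

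**Working it through.** **Step 1: apply the written rule to individual patterns.** The SAP states no figure to reproduce. The table follows one parameter.

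| Grade before dosing | Worst grade after dosing | Tabulated as | Worse than baseline? |
|---|---|---|---|
| 0 | 2 | Grade 2 | Yes |
| 1 | 2 | Grade 2 | Yes |
| 2 | 2 | Grade 2 | No |
| 2 | 1 | Grade 1 | No, improved |
| 2 | 0 | Not graded if the label governs; Grade 2 if the definition is read literally | No, resolved |

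The first three rows give the same entry. The fourth subject, who improved, is entered like one who moved from Grade 0 to Grade 1. The last row shows the ambiguity in the definition.

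**Step 2: ask whether another planned laboratory output makes the link.**
- Change from baseline is summarised for continuous values by visit. It does not show which subjects crossed a grade boundary.
- By-visit counts of significant abnormalities may show a baseline column, but they give group totals and do not connect a subject's baseline status with later status.
- Line plots and listings hold the information, but the reader must extract it subject by subject and parameter by parameter.

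No planned laboratory table cross-classifies baseline grade with later grade.

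**Step 3: illustrate the size.** Inputs: n = 3 active subjects in each of Cohorts 1 to 3 and n = 15 in Cohort 4 (SAP Sections 3.4 and 3.6). Let p be the share of subjects with a graded abnormality in a given parameter that is present before dosing and persists afterwards without worsening. The SAP gives no value, so p is an assumption, and subjects are taken as independent.

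Expected number counted without worsening = n × p. Chance of at least one = 1 − (1 − p)^n.

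| p (assumed) | n = 3: expected | n = 3: at least one | n = 15: expected | n = 15: at least one |
|---|---|---|---|---|
| 5% | 0.15 | 14% | 0.75 | 54% |
| 10% | 0.3 | 27% | 1.5 | 79% |
| 20% | 0.6 | 49% | 3.0 | 97% |
| 30% | 0.9 | 66% | 4.5 | 99.5% |

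For example, with n = 15 and p = 10%: 15 × 0.10 = 1.5 and 1 − 0.9^15 = 0.794. With p = 30%: 15 × 0.30 = 4.5 and 1 − 0.7^15 = 0.995.

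**Step 4: after the change.** In a count restricted to grades above baseline, all of these subjects contribute 0, whatever p is.

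**The case against.** The strongest defence is that the SAP promises a worst post-baseline grade and delivers one. It does not call the grades treatment-emergent or drug-related, and toxicity grade is ordinary grading vocabulary. Baseline status can be seen elsewhere: with 3 subjects, a line plot shows every trajectory, and a grade-by-grade grid would be mostly empty. No decision rests on the table. The primary endpoint is treatment-emergent adverse events, which already have a new-or-worsened rule, and cohort expansion turns on adverse events of interest and dose-limiting toxicities. The ECG shift uses a three-category investigator assessment, not CTCAE grades, so it is not an exact precedent. The SAP also notes that the study was closed early and that some outputs may not be needed.

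Most of this stands, and it limits the point to presentation. It does not remove it, because no planned laboratory table shows who worsened in grade.

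A reader might go further and infer that pre-existing abnormalities will dominate the counts, or that drug effect cannot be separated from underlying disease. The documents do not support that:
- The study is randomised, and the tables carry a pooled placebo column. Eight placebo subjects are planned (1 + 1 + 1 + 5), plus those enrolled under Amendment 5. Persisting abnormalities are expected there too: at the same assumed 10% to 30%, 0.8 to 2.4 of 8. The comparison is imprecise, but it exists, and a shift table has the same small numbers.
- The chance of at least one such count says nothing about a difference between arms. With 3 subjects and p = 10%, the chance of none is 0.9^3 = 73%.
- The size of p is unknown. The SAP sets no threshold for a potentially clinically significant laboratory result and cites the CTCAE criteria without reproducing them. Any eligibility limits on laboratory values would be in the protocol, which is not at hand.

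**Conclusion.** The point holds as a shortcoming of one descriptive safety table. As written, Section 9.3 cannot distinguish persisting or improving laboratory abnormalities from new or worsened ones, and its definition of the worst grade does not clearly exclude pre-dose samples. Only abnormalities that are still graded after dosing are affected, unless the definition is read literally. The range of 1.5 to 4.5 of 15 Cohort 4 active subjects per parameter is conditional on an assumed 10% to 30% and is not an estimate for this trial.

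The consequence is possible misreading. The data are collected and listed, the primary endpoint is handled correctly on this point, and no escalation rule in the SAP depends on laboratory grades. A reader might take the table to attribute pre-existing abnormalities to the drug, but the SAP makes no such attribution. The change is still worth making: it is cheap, it serves the primary objective, and it matches the reference to baseline that the SAP already uses for adverse events, ECG assessments and some vital signs.

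**What to change.** In Section 9.3:
1. Present, for each parameter, baseline grade by worst grade after the first dose of study drug (AP-PA02 or placebo), using scheduled and unscheduled samples, by dose group and pooled placebo.
2. Separate the high and low directions where a parameter is graded in both.
3. Add a line counting subjects whose grade worsened from baseline.
4. For parameters without a CTCAE scale, use the same layout with low, normal and high against the laboratory range.
5. Define post-baseline as after the first dose, and replace the wording that refers to the whole study.

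The cost is one extra table layout and its programming. Section 6.2.1 already defines baseline, and baseline laboratory values are collected. Cells will be sparse in the 3-subject cohorts, where the line for worsened grade will be the most useful part. If the reduced reporting after early closure leaves no room for the full grid, that line alone would cover the main need.

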9.3.1. Hematology

Hematology will include a complete blood count (CBC), which includes hematocrit, hemoglobin, platelet count, and WBC (with absolute and/or relative differential of neutrophils, bands, lymphocytes, monocytes, eosinophils, basophils).

9.3.2. Serum Chemistry

Serum chemistries will include albumin, sodium, potassium, chloride, bicarbonate, blood urea nitrogen (BUN), creatinine, glucose, calcium, phosphorus, alkaline aminotransferase (ALT), aspartate aminotransferase (AST), alkaline phosphatase, bilirubin (total and direct). Creatinine clearance is to be calculated using the Cockcroft-Gault equation adjusted for actual body weight.

9.3.3. Urinalysis

Urinalysis will be performed at time points designated by the study schedule at the local laboratory. Urinalysis will be performed by visual inspection and dipstick, and will include color and appearance, specific gravity, pH, protein, glucose, occult blood, ketones, bilirubin, leukocyte esterase, nitrite, and urobilinogen. In addition, microscopic analyses will be performed on samples with abnormal dipstick results.

9.3.4. Coagulation

Coagulation testing (PT-INR, PTT) to be performed at Screening for eligibility.

9.4. Vital Signs

Vital sign measurements will consist of heart rate, respiratory rate, pulse, blood pressure (systolic and diastolic), temperature and oximetry. Descriptive summaries (number of subjects, mean, standard deviation, median, minimum, and maximum) of actual values and changes from pre-dose will be presented for each visit and time point, by study part and dose group. These summaries will be presented for the safety population and by dose cohort. Vital signs will be performed at prespecified time points per the Schedule of Assessments in Appendix 1 of the Protocol.

This document is confidential.

Temperature will be summarized in Celsius (C) units. Fahrenheit (F) will be converted to Celsius using the following conversion:

$$(\text{Temperature (F)} - 32) * 5/9 = \text{Temperature (C)}$$

Potentially clinically significant (PCS) vital sign abnormalities will be categorized based on Table 10.4.1, and summarized by study part, dose group and assessment visit.

Table 10.4.1: Potentially Clinically Significant Values for Vital Signs

Vital Sign Parameter	Units	Criteria for PCS Values (Observed values)		Criteria for PCS values (Change from Baseline values)	
		High	Low	Increase	Decrease
Heart rate (sitting)	Beats/min	>120	<40	NA	NA
Systolic Blood Pressure (sitting)	mmHg	>180	<90	≥30	≥30
Diastolic Blood pressure (sitting)	mmHg	>110	<50	≥20	≥20
Oxygen Saturation (sitting)	%	NA	<92	≥5	≥5

Vital signs data will be listed chronologically by subject and visit for each vital sign parameter.

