3.6. Determination of Sample Size

The sample size is not based on power calculations; it is chosen based on clinical experience and considered to be adequate to fulfill the objectives of the study.

Eight subjects were planned to be enrolled in the SAD portion of the study, with 4 subjects per cohort (3 AP-PA02 and 1 placebo).

Approximately 24 subjects will be enrolled in the MAD portion of the study, with 4 subjects in Cohort 3 (3 AP-PA02 and 1 placebo) and 20 subjects in Cohort 4 (15 AP-PA02 and 5 placebo). The exact number of subjects enrolled is dependent on whether any dose level is to be expanded due to the occurrence of dose-limiting toxicities (DLT).

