The eight respiratory symptom items will be rescored, summed, and converted to a 0 to 100 scale using the scoring guidelines of the Cystic Fibrosis Respiratory Symptom Diary (CFRSD) and Chronic Respiratory Infection Symptom Scale (CFRSD-CRISS), Version 2.0, 8 September 2016. The CFRSD-CRISS will not be calculated if more than one item response is missing. Scoring of the emotional and activity impact items is still under development and will not be summarized. The rescaling schema and conversion table are provided in [Appendix 15.2](#). CFRSD severity score and absolute changes from baseline will be summarized for visits 2 through 6/EOS for SAD cohorts, and visits 2 through 8/EOS for MAD cohorts using summary statistics.

For SAD Visits 3, 4, 5, 6 and MAD Visits 6, 7, 8, 9 for Cohort 3 and MAD visits 11, 12, 13, and 14 for Cohort 4 under Protocol Version 6, there will be multiple days of diary data. The average daily score will be calculated for these multiple days and presented for a single visit corresponding to the Schedule of Assessments in Appendix 1 of the Protocol. Results for Daily Symptom Diary will be grouped to a single study visit if it occurs on the day of the study visit up until the day before the next visit is performed. For example, if a subject's Visit 3 occurs on Study Day 3, and Visit 4 occurs on Study Day 8, then the Daily Symptom Diary results for Study Day 3, 4, 5, 6, and 7 will be averaged and summarized for Visit 3.

This document is confidential.

9. Safety

The population used for safety analyses will be the Safety Population. Safety will be assessed on the basis of treatment emergent adverse event (TEAE), dose-limiting toxicities (DLTs), vital signs, laboratory assessments, immunogenicity, electrocardiogram (ECG) parameters, and physical examinations.

All safety information will be provided in subject listings.

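### Table 10.4.1 classes a rise in oxygen saturation of 5 or more as a potentially clinically significant abnormality, although the same row treats no high saturation as abnormal

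*SAP*

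**What the plan says.** SAP Section 9.4 sends vital signs to a table of thresholds: "Potentially clinically significant (PCS) vital sign abnormalities will be categorized based on Table 10.4.1". The same sentence has the results tabulated for each study part, dose group and visit. Values that meet a criterion are therefore called abnormalities and reported as such.

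The table has two criteria columns for observed values (High, Low) and two under the heading "Criteria for PCS values (Change from Baseline values" (Increase, Decrease). The row at issue reads "Oxygen Saturation (sitting) % NA <92 ≥5 ≥5". In column order this gives High = NA, Low <92, Increase ≥5 and Decrease ≥5, with the unit given as %.

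The opening of Section 9 makes vital signs part of the safety assessment: "Safety will be assessed on the basis of treatment emergent adverse event (TEAE), dose-limiting toxicities (DLTs), vital signs, laboratory assessments". Section 9.2.1 lists hypoxia among the adverse events of interest and lists no event of high saturation. Nothing in Section 9.4 exempts increases in saturation or says that they are shown as improvement.

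**The concern.** A criterion for a potentially clinically significant value should mark a direction in which a value could be harmful. For oxygen saturation, the High cell says that no value is too high. The Increase cell nevertheless flags a large rise. Followed literally, the rule gives an abnormality label to a subject whose oxygenation has recovered.

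The primary objective of both study parts is safety and tolerability, the product is inhaled, and loss of oxygenation is the named worry. In the vital-sign safety table a gain in oxygenation would carry the same label as a loss. A reader of that table would have to know about the anomaly to discount it.

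**Working it through.** There is no sample-size, power or error-rate figure to reproduce here. Section 3.6 states "The sample size is not based on power calculations", and the PCS outputs are descriptive. The check is a reading of the tables plus simple arithmetic.

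**Step 1: column alignment.** Each row of Table 10.4.1 has four criteria cells, so the first ≥5 in the oxygen saturation row falls under Increase. The row is intact and the reading does not come from a broken table.

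**Step 2: compare the rows (Tables 10.4.1 and 10.5.1).**

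| Parameter | High | Low | Increase | Decrease |
|---|---|---|---|---|
| Heart rate | >120 | <40 | NA | NA |
| Systolic pressure | >180 | <90 | ≥30 | ≥30 |
| Diastolic pressure | >110 | <50 | ≥20 | ≥20 |
| Oxygen saturation | NA | <92 | ≥5 | ≥5 |
| QT, QTcF | three bands from >450 | NA | two bands from ≥30 | NA |

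- Both blood pressure rows are active in both directions, for observed values and for change.
- Heart rate has no change criteria.
- QT/QTcF is NA for Low and NA for Decrease, so a direction of no concern is NA in both places.
- Oxygen saturation alone has a direction that is NA for observed values and active for change.

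**Step 3: who can meet the Increase criterion.** Saturation cannot exceed 100%.

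- Read as percentage points: baseline + 5 ≤ 100, so baseline ≤ 95%.
- Read as relative change: 1.05 × baseline ≤ 100, so baseline ≤ 100/1.05 = 95.2%.

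The table does not say which reading applies. Points is the natural one. Under either reading the criterion can flag only subjects who began at about 95% or lower and then rose.

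**Step 4: two assumed subjects, in percentage points.**

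| Baseline to post-dose | Change | Current table | Increase set to NA |
|---|---|---|---|
| 91% to 96% | +5 | Flagged (Increase) | Not flagged |
| 97% to 92% | −5 | Flagged (Decrease) | Flagged (Decrease) |

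The first subject meets Low at baseline (91 < 92), meets no observed-value criterion after dosing, and is flagged only because of the recovery. The second subject is treated the same either way. Setting the Increase cell to NA loses no desaturation flag, since Low and Decrease do not depend on it.

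**Step 5: weight of one case.** With the planned active numbers in Sections 3.4.1 and 3.4.2, one flagged rise is 1/3 = 33.3% of Cohort 1, 2 or 3, and 1/15 = 6.7% of Cohort 4. These figures show what a single subject contributes to the Increase category. They are not forecasts. The SAP gives no baseline saturation distribution, and Section 6.1 says that the sponsor decided to close the study early.

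**The case against.** The strongest case on the other side has four parts.

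- **No pooled count is defined.** A reader might infer that the number of subjects with PCS vital signs is inflated by improvements and that desaturation is obscured. The SAP does not support this. Abnormalities are categorized by a table that keeps Increase and Decrease apart, and Section 9.4 defines no any-PCS total. Sections 9.5 and 9.7, by contrast, add a summary over all post-baseline times for ECG and spirometry, and Section 9.4 has no such line. If each criterion has its own row, the Low and Decrease counts are untouched. This part stands.
- **Change columns ignore the end value by design.** A systolic pressure going from 85 to 115 mmHg also leaves Low (<90) and meets Increase (≥30). This is true, so the 91% to 96% example is not decisive alone. For blood pressure, however, high values are also abnormal by the table. For saturation they are not, and that mismatch remains.
- **No decision depends on it.** A reader might take the flag for a formal safety signal. The SAP's label is a descriptive screen. Cohort expansion turns on Grade 3 or higher adverse events of interest, and escalation also takes in other respiratory events and the Safety Monitoring Committee's review (Sections 9.2.1 and 10). Hypoxia has its own adverse-event summaries. This part stands.
- **Direction stays visible elsewhere.** Section 9.4 also summarizes actual values and changes from pre-dose, and lists the data by subject. This limits the harm but does not justify the label.

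**Conclusion.** The point holds as an internal inconsistency in one table cell. Table 10.4.1 categorizes a rise in oxygen saturation of 5 or more as a potentially clinically significant abnormality, although its High cell says that no high saturation is abnormal. This departs from the pattern of every other row in Tables 10.4.1 and 10.5.1.

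The consequence is minor. Improvement is tabulated as an abnormality in a descriptive safety output, and no test or stated escalation rule is affected. Mixing of improvement with desaturation is possible only if the directions are pooled, and the SAP does not say whether they are. How often the flag would occur cannot be derived from the document, so the 33.3% and 6.7% figures should not be read as an expected distortion.

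The 95% bound assumes that ≥5 means percentage points. The direction problem does not depend on that assumption.

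**What to change.** In Table 10.4.1, reconcile the oxygen saturation Increase cell with High = NA by setting it to NA. Leave Low (<92) and Decrease (≥5) as they are. If the sponsor still wants large rises shown, report them separately from Low and Decrease and do not label them abnormalities.

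The cost is one table cell and the matching line of the output program. No new data are needed, and every desaturation flag is kept.

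### The planned vital-sign abnormality table is by visit only and generally leaves out unscheduled readings, so it cannot give the number of subjects with an abnormal value after dosing

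*SAP*

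**What the plan says.** Section 9.4 of the SAP uses two layouts for the same vital-sign data.

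- **Descriptive statistics.** Readings follow a schedule with time points: "Vital signs will be performed at prespecified time points per the Schedule of Assessments in Appendix 1 of the Protocol". Actual values and "changes from pre-dose will be presented for each visit and time point".
- **Abnormality counts.** "Potentially clinically significant (PCS) vital sign abnormalities will be categorized based on Table 10.4.1, and summarized by study part, dose group and assessment visit". No time point and no row across visits is mentioned.

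Section 6.4 governs which readings enter tables. It opens with "For data with repeated observations at a given visit, for example, laboratory assessments", for which "the earliest of the available non-missing values at a visit should be used in summary tables"; the other repeats are treated as unscheduled. Then "the unscheduled post-baseline values generally will be excluded from summary tables, but will be included in the listing". The one exception it states is: "Unscheduled visits will be considered for analyses of worst CTCAE laboratory grades".

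Other safety domains are handled differently. In Section 9.5, ECG PCS "values will be summarized by visit/timepoint and for any time post-baseline", and Section 9.7 does the same for FEV1. Section 9.3 also counts laboratory abnormalities by visit, but for hematology and chemistry it adds a worst post-baseline grade taken over scheduled and unscheduled visits.

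**The concern.** Safety and tolerability are the primary objective, and Section 9 names vital signs among the bases of the safety assessment. The natural question for this table is how many subjects in a dose group had an abnormal reading after dosing. As planned, the table falls short in two ways.

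1. A subject rechecked off schedule, for example because of symptoms, can have an abnormal reading that never enters the table.
2. Counts by visit do not add up to subjects. The same person can appear in several rows, or different people can.

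Table 10.4.1 covers heart rate, blood pressure and oxygen saturation. These measurements bear on three of the five adverse events of interest in Section 9.2.1 (hypotension, hypoxia, tachycardia), although the cut-offs do not define those events. A tabulated count from measured values would complement investigator-reported events.

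**Working it through.** The SAP gives no figure on this point to reproduce, so the check compares the text and then looks at what the layout can show.

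**1. Side-by-side comparison**

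| Domain (SAP section) | By time point? | Any-time or worst post-baseline count? | Unscheduled readings expressly included? |
|---|---|---|---|
| Vital-sign PCS (9.4) | No, by visit | No | No; Section 6.4 generally excludes them |
| ECG PCS (9.5) | Yes | Yes | Not stated |
| FEV1 PCS (9.7) | Yes | Yes | Not stated for the table; included in the line plot |
| Hematology and chemistry (9.3) | No, by visit | Yes, worst grade | Yes |

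Vital signs are the only row with neither an any-time count nor a worst-value count.

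**2. Criteria affected (Table 10.4.1)**

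- Observed values: heart rate 2 + systolic 2 + diastolic 2 + oxygen saturation 1 = 7.
- Change from baseline: systolic 2 + diastolic 2 + oxygen saturation 2 = 6.
- Total: 7 + 6 = 13 criteria, none with an any-time count.

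**3. Number of rows in Cohort 4**

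Section 3.4.2 gives ten consecutive dosing days. Section 8.2.5 numbers the later Cohort 4 visits 11 to 14. Taking the dosing days as Visits 1 to 10, there are 10 + 4 = 14 visits.

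**4. What by-visit counts reveal about subjects**

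Let c_i be the number of subjects flagged at visit i, N the group size and D the number of distinct subjects flagged at any scheduled visit. Then

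max(c_i) ≤ D ≤ min(N, Σ c_i).

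Illustration with N = 15 (planned Cohort 4 active subjects, Section 3.4.2) and c_i = 1 in each of the ten dosing-day rows, zero elsewhere:

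- Lower bound: max(c_i) = 1, so 1/15 = 6.7%.
- Upper bound: min(15, 10) = 10, so 10/15 = 66.7%.

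The pattern is chosen to show the layout's limit and is not a forecast. It assumes vital signs on every dosing day (the schedule is in the protocol, not shown) and full enrolment. Section 6.1 records a decision to close the study early, so N may be smaller. Off-schedule readings are outside these bounds, because the table generally does not contain them.

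**The case against.** **The SAP promises no any-time count for vital signs, so nothing is contradicted.** This is true. The point concerns a better rule, and the SAP already uses its parts elsewhere. ECG is a modest comparator, since Section 9.5 lists only one post-dose recording (1 hour, Day 1), and neither the ECG nor the FEV1 table expressly includes unscheduled readings. That inclusion is borrowed from the laboratory rule in Section 9.3.

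**Other outputs carry the information.** This largely stands. All readings are listed by subject, scheduled extremes appear as minimum and maximum by time point, and hypotension, hypoxia and tachycardia reported as adverse events are counted once per subject. However, a minimum or maximum does not say how many subjects were affected, and a listing leaves the reader to count by hand.

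**A stronger reading.** A reader might infer that the earliest-value rule in Section 6.4 fills each dosing-day row with the first reading, pre-dose on Day 1, so that abnormalities after inhalation are dropped. The text makes this unlikely. The rule concerns repeated observations and turns the surplus ones into unscheduled visits; prespecified time points are scheduled. Applied to them, it would clash with the visit-and-time-point summaries in Section 9.4 itself. That Section 9.4 does not say how time points combine within a visit is missing detail, which a programming note could settle.

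**An any-time percentage brings its own bias.** This stands. Section 6.1 puts Amendment 5 subjects into pooled placebo, so even among multiple-dose subjects it mixes 3-, 5- and 10-day regimens. Cohort 4 active subjects probably have more chances of a flag than many placebo subjects.

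**Conclusion.** The point holds as a cheap improvement of minor to moderate weight. Under Sections 9.4 and 6.4 as written, the vital-sign PCS table generally omits abnormal readings taken off schedule, and it cannot give the number of distinct subjects with a PCS value after dosing. The word *generally* in Section 6.4 allows exceptions, but none is stated for vital signs.

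The size is a loss of information in one table, across 13 criteria. The 6.7% to 66.7% range shows only how loosely visit rows can bound a subject count, and rests on the assumptions stated with it. No data are lost. The listings, time-point minimum and maximum, and counts of treatment-emergent adverse events and dose-limiting toxicities are unaffected.

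**What to change.** Replace the PCS sentence in Section 9.4 with:

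> The number and percentage of subjects with PCS vital-sign values (Table 10.4.1) will be summarized by study part, dose group and visit/timepoint (for repeats at one time point, the Section 6.4 rule applies), and for any time post-baseline, where a subject is counted if any scheduled, repeat or unscheduled post-baseline reading meets the criterion.

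Keeping Section 6.4 for repeats at one time point matters, because switching it off entirely would leave those rows without a selection rule.

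Add a footnote that any-time percentages for Cohort 4 against pooled placebo reflect different numbers of assessments per subject and should be read beside the visit/timepoint rows.

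The cost is one sentence, one footnote and minor programming on data already collected. The downside is more incidental flags in the any-time row, especially in the ten-day cohort.
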